10.4 Response Criteria

10.4.1 Evaluation of Target Lesions

Complete Response (CR): Disappearance of all target lesions. Any pathological lymph nodes (whether target or non-target) must have reduction in short axis to <10 mm.

Partial Response (PR): At least a 30% decrease in the sum of the diameters of target lesions, taking as reference the baseline sum diameters.

Progressive Disease (PD): At least a 20% increase in the sum of the diameters of target lesions, taking as reference the smallest sum on study (this includes the baseline sum if that is the smallest on study). In addition to the relative increase of 20%, the sum must also demonstrate an absolute increase of at least 5 mm. (Note: the appearance of one or more new lesions is also considered progressions).

Stable Disease (SD): Neither sufficient shrinkage to qualify for PR nor sufficient increase to qualify for PD, taking as reference the smallest sum diameters while on study.

10.4.2 Evaluation of Non-Target Lesions

Complete Response (CR): Disappearance of all non-target lesions and normalization of tumor marker level. All lymph nodes must be non-pathological in size (<10 mm short axis).

Note: If tumor markers are initially above the upper normal limit, they must normalize for a patient to be considered in complete clinical response.

Non-CR/Non-PD: Persistence of one or more non-target lesion(s) and/or maintenance of tumor marker level above the normal limits.

Progressive Disease (PD): Appearance of one or more new lesions and/or unequivocal progression of existing non-target lesions. Unequivocal progression should not normally trump target lesion status. It must be representative of overall disease status change, not a single lesion increase.

Although a clear progression of “non-target” lesions only is exceptional, the opinion of the treating physician should prevail in such circumstances, and the

progression status should be confirmed at a later time by the review panel (or Principal Investigator).

10.4.3 Evaluation of Best Overall Response

The best overall response is the best response recorded from the start of the treatment until disease progression/recurrence (taking as reference for progressive disease the smallest measurements recorded since the treatment started). The patient's best response assignment will depend on the achievement of both measurement and confirmation criteria.

For Patients with Measurable Disease (i.e., Target Disease)

Target Lesions	Non-Target Lesions	New Lesions	Overall Response	Best Overall Response when Confirmation is Required*
CR	CR	No	CR	>4 wks. Confirmation**
CR	Non-CR/Non-PD	No	PR	>4 wks. Confirmation**
CR	Not evaluated	No	PR	
PR	Non-CR/Non-PD/not evaluated	No	PR	
SD	Non-CR/Non-PD/not evaluated	No	SD	Documented at least once >4 wks. from baseline**
PD	Any	Yes or No	PD	no prior SD, PR or CR
Any	PD***	Yes or No	PD	
Any	Any	Yes	PD	

* See RECIST 1.1 manuscript for further details on what is evidence of a new lesion.

** Only for non-randomized trials with response as primary endpoint.

*** In exceptional circumstances, unequivocal progression in non-target lesions may be accepted as disease progression.

Note: Patients with a global deterioration of health status requiring discontinuation of treatment without objective evidence of disease progression at that time should be reported as "symptomatic deterioration." Every effort should be made to document the objective progression even after discontinuation of treatment.

For Patients with Non-Measurable Disease (i.e., Non-Target Disease)

Non-Target Lesions	New Lesions	Overall Response
CR	No	CR
Non-CR/non-PD	No	Non-CR/non-PD*
Not all evaluated	No	not evaluated
Unequivocal PD	Yes or No	PD
Any	Yes	PD

* ‘Non-CR/non-PD’ is preferred over ‘stable disease’ for non-target disease since SD is increasingly used as an endpoint for assessment of efficacy in some trials so to assign this category when no lesions can be measured is not advised

10.4.4 Duration of Response

Duration of overall response: The duration of overall response is measured from the time measurement criteria are met for CR or PR (whichever is first recorded) until the first date that recurrent or progressive disease is objectively documented (taking as reference for progressive disease the smallest measurements recorded since the treatment started).

The duration of overall CR is measured from the time measurement criteria are first met for CR until the first date that progressive disease is objectively documented.

Duration of stable disease: Stable disease is measured from the start of the treatment until the criteria for progression are met, taking as reference the smallest measurements recorded since the treatment started, including the baseline measurements.

11 DATA AND SAFETY MONITORING

In compliance with the Washington University Institutional Data and Safety Monitoring Plan, the Principal Investigator will provide a Data and Safety Monitoring (DSM) report to the Washington University Quality Assurance and Safety Monitoring Committee (QASMC) semi-annually beginning six months after accrual has opened (if at least five patients have been enrolled) or one year after accrual has opened (if fewer than five patients have been enrolled at the six-month mark).

The Principal Investigator will review all patient data at least every six months, and provide a semi-annual report to the QASMC. This report will include:

- HRPO protocol number, protocol title, Principal Investigator name, data coordinator name, regulatory coordinator name, and statistician
- Date of initial HRPO approval, date of most recent consent HRPO approval/revision, date of HRPO expiration, date of most recent QA audit, study status, and phase of study
- History of study including summary of substantive amendments; summary of accrual suspensions including start/stop dates and reason; and summary of protocol exceptions, error, or breach of confidentiality including start/stop dates and reason

- Study-wide target accrual and study-wide actual accrual
- Protocol activation date
- Average rate of accrual observed in year 1, year 2, and subsequent years
- Expected accrual end date
- Objectives of protocol with supporting data and list the number of participants who have met each objective
- Measures of efficacy
- Early stopping rules with supporting data and list the number of participants who have met the early stopping rules
- Summary of toxicities
- Abstract submissions/publications
- Summary of any recent literature that may affect the safety or ethics of the study

The study principal investigator and Research Patient Coordinator will monitor for serious toxicities on an ongoing basis. Once the principal investigator or Research Patient Coordinator becomes aware of an adverse event, the AE will be reported to the HRPO and QASMC according to institutional guidelines.

12 STATISTICAL CONSIDERATIONS

12.1 Stopping Criteria

If at any point in trial enrollment, >2 out of the first 5 patients, or >4 out of the first 10 patients experience symptoms of G3 or greater toxicity that is probably or definitely attributable to and did not pre-date SBRT, the trial will be suspended. Symptoms that pre-dated SBRT will not be count towards stopping criteria (example: thoracic spine patients requiring oxygen prior to and after SBRT will not be scored as G3 toxicity, however a new O2 requirement after RT would count towards stopping criteria). If at any time a grade 5 toxicity (death) is observed that is probably or definitely attributable to treatment, accrual will be suspended and the event will be reviewed by the principal investigator. Since patients accruing to the trial have metastatic disease, it is anticipated that deaths unrelated to the trial may be observed. Death that is felt either due to disease progression or patient comorbidity will not be scored as grade 5 toxicity and will not result in trial suspension.

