4.5 Strategies for Recruitment and Retention

Patients will be accrued on basis of presentation to the radiation oncology clinic with spinal metastasis amenable to SBRT. Potential participants will be identified in the inpatient and outpatient radiation oncology clinic setting, as well as from the multidisciplinary spine tumor board. Patients will be approached regarding participation at or around the time of

their radiation oncology consultation visit. Patients will be treated at a single facility, at the Siteman Cancer Center's Center for Advanced Medicine clinic, as the technology required for this study is confined to this center. We anticipate an accrual rate of approximately 15 patients per year, or an estimated study accrual period of 8-12 months. There will be no compensation or incentives offered for study participation.

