5.3 Definitions of Evaluability

Endpoint	In order to be evaluable for this endpoint, a patient must have...
Primary: Feasibility	Received simulation
Exploratory: Time from consult to delivery of first fraction	Had a consult and received at least 1 fraction of RT
Exploratory: Local, in-field tumor response rates at 3 mos	Received any study treatment and undergone volumetric imaging at 3 mos
Exploratory: Local, in-field tumor control rate at 3 mos	
Exploratory: Grade 3 or higher toxicity	Received any study treatment
Exploratory: Dosimetric differences between MRI-only planning using standard bulk density override dose calculations and voxel-by-voxel MRI-based dose calculation using MLA	Received MRI and dose calculated using bulk density vs voxel-by-voxel
Exploratory: On-table time required for initial treatment fraction and subsequent treatment fractions	Received at least 1 fraction of RT

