8 STUDY CALENDAR

	Screening	Pre-Treatment	D1	D2	D3	D4	D5	3 mos post-SBRT ¹
Informed consent	X							
Medical history	X							
Volumetric imaging	X ⁵							X
Pregnancy test ²	X							
Adaptive SBRT			X	X	X ³	X ³	X ³	
Adverse events assessment		X	X -----X					

1. Window is 10-14 weeks post-completion of SBRT

2. Women of childbearing potential only; within 14 days of start of treatment

3. Treatment days 3,4,5 are for a 5-fraction course of treatment only. If a 2-fraction course is selected, then there would be only two treatment days.

5. Collection of a standard of care diagnostic CT scan completed in the past 6 months

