12.2 Sample Size Calculation

As a pilot study, the sample size is determined based on clinical considerations rather than statistical power. For our primary objective, our goal will be to report the description of same-session MR-only simulation and treatment with SMART treatment workflows, adaptation, and the time to delivery of first treatment fraction. Goal accrual will be 10 evaluable patients. For the secondary objectives, sample size is also based on clinical considerations rather than statistical power.

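### The toxicity stopping rule sets no count between the first 5 and the first 10 patients, and 10 is the whole planned accrual, so enrolment may continue at 50–57% observed Grade 3+ toxicity at patients 6 to 8

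*Combined protocol and SAP*

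**What the plan says.** Section 12.1 (Stopping Criteria) sets the count rule: "If at any point in trial enrollment, >2 out of the first 5 patients, or >4 out of the first 10 patients" have Grade 3 or greater toxicity that is "probably or definitely attributable to and did not pre-date SBRT, the trial will be suspended". In whole numbers, the trial is suspended at 3 or more of the first 5, or 5 or more of the first 10. No count is attached to 6, 7, 8 or 9 patients.

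The same section has a separate trigger for deaths: "If at any time a grade 5 toxicity (death) is observed that is probably or definitely attributable to treatment, accrual will be suspended".

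Section 12.2 (Sample Size Calculation) states: "Goal accrual will be 10 evaluable patients". It adds that "the sample size is determined based on clinical considerations rather than statistical power". The documents give no acceptable or unacceptable toxicity rate and no operating characteristics for the rule.

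On timing, Section 4.5 says: "We anticipate an accrual rate of approximately 15 patients per year, or an estimated study accrual period of 8-12 months". The Synopsis instead allows 48 months for accrual. Toxicity is followed to one visit after treatment, and the Study Calendar (Section 8) notes: "Window is 10-14 weeks post-completion of SBRT". No pause in enrolment is described.

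Section 11 adds continuing review of serious toxicity by the principal investigator and the coordinator, without a numeric limit. The data and safety monitoring tables in Appendix E answer No to the question whether early stopping rules exist, which contradicts Section 12.1.

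**The concern.** A rule that suspends enrolment protects only patients who have not yet been treated. Here the second denominator equals the planned sample. If the fifth event comes only with patient 10, nobody is left for the suspension to protect. Between patients 6 and 9 no intermediate count applies. If the first five patients contribute two events or fewer, the trial can carry on with half or more of its treated patients having an attributable Grade 3 or 4 event.

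Section 12.3 names safety beside feasibility as a principal aim, and Section 1.5 calls the workflow novel. The Grade 3+ count is the plan's only trigger based on accumulating non-fatal toxicity, so how it behaves in the second half of a ten-patient trial matters.

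**Working it through.** **Inputs.** Limits: 3 of the first 5 and 5 of the first 10, checked at any point (Section 12.1). Planned accrual: 10 (Section 12.2). True Grade 3+ rates p of 10 to 50% are my assumptions. The documents state no probability for this rule, so there is no figure to reproduce.

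**Step 1: highest count that does not suspend.** Let X(n) be the number of qualifying patients among the first n. Enrolment continues while X(5) ≤ 2 and the running total is ≤ 4.

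| Patients treated | Highest count without suspension | Observed rate |
|---|---|---|
| 5 | 2 | 40% |
| 6 | 3 | 50% |
| 7 | 4 | 57% |
| 8 | 4 | 50% |
| 9 | 4 | 44% |
| 10 | 4 | 40% |

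The two limits themselves trip at 3/5 = 60% and 5/10 = 50%. At patients 6 to 8 the permitted rate is therefore at or above the rate that trips the ten-patient limit; at patient 9 it is below it. With at most two events in the first five, the ten-patient limit needs three more, so it can trip no earlier than patient 8 (5/8).

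**Step 2: what the ten-patient limit adds before patient 10.** With events known at once,

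P(suspended before patient 10) = P(X(5) ≥ 3) + P(X(5) ≤ 2 and X(9) ≥ 5).

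The second term is P(X(5)=1)·P(Y=4) + P(X(5)=2)·P(Y≥3), where Y is binomial on patients 6 to 9. At p = 0.4:

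- five-patient limit: 0.317
- ten-patient limit: 0.2592 × 0.0256 + 0.3456 × 0.1792 = 0.0066 + 0.0619 = 0.069
- total: 0.386

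**Step 3: the rule with an added limit of more than 3 of the first 8.** X(9) ≥ 5 requires X(8) ≥ 4, so

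P(suspended before patient 10) = P(X(5) ≥ 3) + P(X(5) ≤ 2 and X(8) ≥ 4).

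At p = 0.4 the second term is 0.2592 × 0.064 + 0.3456 × 0.352 = 0.0166 + 0.1217 = 0.138, and the total is 0.317 + 0.138 = 0.456 (from unrounded terms).

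| True rate | Five-patient limit alone | Added by ten-patient limit | As written | With more than 3 of 8 added | More than 40% at every count from 5 to 9 |
|---|---|---|---|---|---|
| 10% | 0.9% | under 0.1 points | 0.9% | 1.1% | 2.7% |
| 20% | 5.8% | 0.6 points | 6.4% | 8.2% | 15.9% |
| 30% | 16.3% | 2.9 points | 19.2% | 23.9% | 38.2% |
| 40% | 31.7% | 6.9 points | 38.6% | 45.6% | 62.2% |
| 50% | 50.0% | 10.7 points | 60.7% | 67.6% | 81.5% |

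All entries are chances of suspension before patient 10. Counting patient 10 as well, the rule as written gives 7.3, 22.5, 45.1 and 68.7% at true rates of 20, 30, 40 and 50%.

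**Step 4: how often the gap is entered.** The chance of being unsuspended at 50% or more observed toxicity somewhere in patients 6 to 8 is 5.1, 12.2, 18.8 and 21.5% at true rates of 20, 30, 40 and 50%.

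**Step 5: delay.** At 15 per year (1.25 per month), 3 × 1.25 = 3.75 patients enter during a three-month follow-up. Ten patients in 48 months is one every 4.8 months, and patient 5 would usually reach the 10–14 week visit before patient 6 enters. The delay thus depends on which accrual figure holds; the gap in Step 1 does not.

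**The case against.** The rule guards more than its two denominators suggest, and several stronger readings fail.

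- A reader might infer that once patient 6 enters, only a fifth event can suspend the trial. Section 12.1 applies both limits at any point in enrolment, so a late third event among the first five still suspends. If follow-up lags behind accrual, that keeps the five-patient limit active for longer. It does not follow that most of the trial is unguarded.
- A reader might infer that the ten-patient limit acts only at full accrual. It can trip from patient 8.
- A reader might call the count rule the only safety trigger. One attributable death also suspends accrual, and Section 11 requires continuing review. The 50–57% paths therefore consist of Grade 3 and 4 events, and they would be seen.
- A reader might say the plan breaches its own 40% limit. No such limit is stated; 40% is inferred from the two counts. A straight line between the trip points of 60% and 50% gives about 58, 56, 54 and 52% at patients 6 to 9, and only 4/7 exceeds it, by about one point.

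It is also fair that this is a ten-patient pilot of a treatment the protocol calls standard of care, with toxicity expected to match other linear-accelerator SBRT (Section 12.3). True rates of 40–50% are stress tests and appear nowhere in the documents.

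All of this limits the size of the point. It does not supply a count for patients 6 to 9, nor explain why the second count was placed where almost no enrolment remains.

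**Conclusion.** The point holds in a limited form. Section 12.1 has no intermediate count, and its second denominator is the entire planned accrual. When no more than two of the first five patients have events, enrolment may continue at 3/6, 4/7 or 4/8. The ten-patient limit adds about 3, 7 and 11 percentage points to the chance of suspension before patient 10 at true rates of 30, 40 and 50%, so as written most of the protection comes from the first five patients.

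The probabilities rest on assumed true rates, independent patients and events known at once. The documents do not support the conclusion that the trial has no protection after patient 5. The gain from closing the gap is modest: about 7 points at true rates of 40 and 50%.

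**What to change.** Add to Section 12.1 an intermediate limit that can act while patients remain to be enrolled, for example suspension if more than 3 of the first 8 patients have a qualifying event, checked at any point, and keep the existing 5- and 10-patient limits. This closes 4/7 and 4/8 but still permits 3/6. The ten-patient limit keeps a role only at patient 10 itself (3/8 followed by two more events).

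Before each registration, record the running count and how many of the counted patients have completed the 3-month visit. State which patients form the denominators: Section 5.3 defines feasibility evaluability as "Received simulation", whereas toxicity evaluability requires study treatment, so the two groups of ten may differ. Reconcile the No in Appendix E with Section 12.1.

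The cost is one sentence, a checklist line and a slightly higher chance of a temporary suspension when toxicity is low: 0.9% to 1.1% at a true rate of 10%, and 6.4% to 8.2% at 20%. The trial is suspended, not closed.

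Applying more than 40% at every count from 5 to 9 is a stricter option. It gives 62% and 81% before patient 10 at true rates of 40 and 50%, against 2.7% and 16% at 10 and 20%. It would suspend at 4/9 although the plan tolerates 4/10, and it would make the ten-patient limit redundant, because 5/10 cannot be reached without at least 4/9. If the investigators prefer no intermediate limit, Section 12.1 should say why.

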Typically, the spine SBRT treatment-planning paradigm is initiated through a simulation (planning) CT and a simulation MRI (or fusion of previously obtained diagnostic MR

image sets). Simulation typically takes place within several business days of the clinical consult appointment, and an additional 1-2 weeks are needed from the time of simulation before a treatment plan is prepared and verified for delivery. Therefore, a patient may not start treatment until two weeks after their consult appointment. This workflow prolongs patient discomfort from painful osseous and nerve pain and increases the opportunity for further threatening of neurologic functions like ambulation and continence as tumors progress. Ideally, this workflow could be substantially compressed through advances in technology and treatment planning processes.

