5.2 Collection of AEs

For all patients, neurologic toxicities of concern include (but are not limited to) treatment-related spinal injury resulting in sensory alteration, muscle weakness, or neuropathic pain limiting self-care in activities of daily living. For patients receiving treatment to lower thoracic and lumbar spine sites, toxicities of concern also include (but are not limited to) gastrointestinal toxicities such as: severe pain, severe nausea or diarrhea, severe constipation, and/or gastrointestinal hemorrhage, stenosis, ulceration, fistula, perforation, etc. Patients undergoing treatment for thoracic metastases will additionally be assessed using the CTCAE v5.0 criteria for lung, esophageal (eg esophagitis), and cardiovascular toxicity. Regardless of treatment site, skin toxicity will be tabulated according to the CTCAE v5.0 criteria.

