7 REGULATORY AND REPORTING REQUIREMENTS

The entities providing oversight of safety and compliance with the protocol require reporting as outlined below. Please refer to Appendix B for definitions and Appendix C for a grid of reporting timelines.

Adverse events will be tracked from start of treatment through the 3-month post-treatment follow-up visit. All adverse events must be recorded on the toxicity tracking case report form (CRF) with the exception of:

- Baseline adverse events, which shall be recorded on the medical history CRF
- Grade 1-2 AEs regardless of relatedness
- Grade 3-4 AEs that predate SBRT
- Grade 3-4 AEs that are not at least probably attributable to treatment

Refer to the data submission schedule in Section 9 for instructions on the collection of AEs in the EDC.

Reporting requirements for Washington University study team may be found in Section 7.1.

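### Section 12.1 excludes pre-existing symptoms without reference to grade, so read literally the rule drops attributable worsening to Grade 3 or higher

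*Combined protocol and SAP*

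**What the plan says.** Section 12.1 sets the count at ">2 out of the first 5 patients, or >4 out of the first 10 patients". Patients are counted if they "experience symptoms of G3 or greater toxicity that is probably or definitely attributable to and did not pre-date SBRT". The next sentence is the exclusion: "Symptoms that pre-dated SBRT will not be count towards stopping criteria". It mentions neither grade nor worsening. Its example has two halves. In the first, "thoracic spine patients requiring oxygen prior to and after SBRT will not be scored as G3 toxicity"; in the second, "however a new O2 requirement after RT would count towards stopping criteria". A separate sentence suspends accrual after a single attributable Grade 5 event.

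Section 7 lists what stays off the toxicity form. One item is "Baseline adverse events, which shall be recorded on the medical history CRF", with no clause for later worsening; Section 9.1 repeats the baseline rule. Another item exempts Grade 3 or 4 events that were already present before SBRT.

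Section 5.2 gives the neurologic toxicities of concern as "treatment-related spinal injury resulting in sensory alteration, muscle weakness, or neuropathic pain limiting self-care in activities of daily living". Section 1.2 says of the conventional planning delay: "This workflow prolongs patient discomfort from painful osseous and nerve pain". Section 3.2 excludes symptomatic cord compression but no lesser neurologic symptom. Section 8 schedules an adverse event assessment before treatment.

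**The concern.** In many trials a rule that ignores pre-existing symptoms would matter little, because the toxicity looks different from the disease. Here the two overlap. Pain, sensory change and weakness are what a spinal metastasis can cause, and also what cord or nerve injury from SBRT would look like. Section 1.4 treats cord dose as the main safety question for this method. In a patient who already has symptoms, such an injury would often appear as worsening and not as a new symptom.

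Take two patients with the same outcome, Grade 3 leg weakness judged probably due to SBRT. One had no weakness at entry and the other had Grade 1. Under the literal exclusion the first counts and the second does not. With thresholds of 3 in 5 and 5 in 10 and a goal of 10 evaluable patients, the classification of one patient can decide whether the trial suspends. As written, that classification would be argued after the event.

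**Working it through.** The plan gives no toxicity rate, error rate or operating characteristic for this rule, so there is no figure of its own to reproduce. The check has two parts.

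**1. The wording, case by case.** Every event after SBRT is taken to be at least probably attributable. Reading A takes the exclusion sentence literally. Reading B takes the counting sentence to mean that the Grade 3+ toxicity itself must not have been present before SBRT.

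| Before SBRT | After SBRT | Reading A | Reading B | Section 7 recording |
|---|---|---|---|---|
| None | Grade 3 | Counts | Counts | Recorded |
| Grade 1-2 | Grade 3 | Discarded | Counts | Outside the Grade 3-4 exception; unclear under the baseline exception |
| Grade 3 | Grade 3 | Discarded | Discarded | Exempt |
| Grade 3 | Grade 4 | Discarded | Unclear | Exempt on its face |

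The oxygen example settles the third row (unchanged requirement, not counted) and shows that a new requirement counts. It does not address the second or fourth row.

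**2. Scale, under assumed rates.** Inputs:
- Thresholds from Section 12.1: at least 3 of the first 5, or at least 5 of the first 10.
- p, the true proportion of patients with attributable Grade 3+ toxicity (assumed).
- f, the share of those patients whose only such event is worsening of a pre-existing symptom (assumed).
- Patients independent with a common rate.

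Under Reading A the countable rate is q = p(1 − f); if worsening counts, q = p. Let X1 and X2 be the counts in the first and second five patients, each Binomial(5, q). Then

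P(suspend) = P(X1 ≥ 3) + P(X1=0)P(X2=5) + P(X1=1)P(X2 ≥ 4) + P(X1=2)P(X2 ≥ 3).

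- p = 0.50, worsening counts (q = 0.50): 16/32 + (1×1 + 5×6 + 10×16)/1024 = 0.5000 + 191/1024 = 0.6865.
- p = 0.50, f = 0.50 (q = 0.25): 0.1035 + 0.0002 + 0.0062 + 0.0273 = 0.1372.
- p = 0.30, worsening counts (q = 0.30): 0.1631 + 0.0004 + 0.0111 + 0.0503 = 0.2249.
- p = 0.30, f = 0.50 (q = 0.15): 0.0266 + 0.0000 + 0.0009 + 0.0037 = 0.0312.

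The same formula over a wider range:

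| True rate p | Worsening counts | f = 25% | f = 50% | f = 75% |
|---|---|---|---|---|
| 20% | 7.3% | 3.1% | 0.9% | 0.1% |
| 30% | 22.5% | 10.2% | 3.1% | 0.4% |
| 40% | 45.1% | 22.5% | 7.3% | 0.9% |
| 50% | 68.7% | 39.0% | 13.7% | 1.8% |

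**The case against.** The best defence is that Reading B is the natural one. What must not pre-date SBRT is the Grade 3+ toxicity, so Grade 1 weakness that becomes attributable Grade 3 counts. The oxygen example fits: a requirement for oxygen is a level of severity, and the half that counts does not demand that the patient had no respiratory symptom before. This stands as a possible reading. A reader might infer from the exclusion sentence that worsening of a pre-existing symptom can never trigger suspension, whatever grade it reaches; the documents do not support that, because the counting sentence permits the opposite. But the exclusion sentence has no grade in it, and the example leaves worsening unaddressed, so the defence shows an ambiguity and does not remove it.

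A reader might also take this for the trial's only safety stop. It is not. An attributable Grade 5 event suspends accrual by itself, and Section 11 provides ongoing monitoring and semi-annual committee reports. It is the only stated suspension rule for non-fatal toxicity.

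Nor does Section 7 clearly remove all such events from the Grade 3+ toxicity endpoint and bias it downward. Its Grade 3-4 exception does not reach a symptom that was Grade 1 or 2 at baseline, and the endpoint in Section 2 carries no pre-dating exclusion. What remains in Section 7 is the silence of the baseline exception on worsening, and the rise from Grade 3 to 4.

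Two further points are fair. Entry does not require symptoms, so the share of patients affected is unknown. And Section 12.3 expects toxicity like that of other linear accelerator SBRT. If the true rate is low, suspension is unlikely under any reading (7.3% at 20%), mainly because of the thresholds.

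**Conclusion.** The point holds as a defect of wording with a safety consequence. Section 12.1 contains two sentences that can classify the same event differently, and the literal sense of the second discards attributable worsening to Grade 3+ in the symptoms that Section 5.2 singles out. Section 7 does not resolve it: it is silent on worsening of baseline events, and on its face it leaves a rise from Grade 3 to 4 unrecorded.

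The size is conditional. If half the affected patients are discarded, the chance of suspension falls from 22.5% to 3.1% at a true rate of 30%, and from 68.7% to 13.7% at 50%. If the investigators already count worsening, the loss is zero. Both p and f are assumptions without support in the documents, so these figures show sensitivity and predict nothing. The case for correction rests on the wording: a suspension rule should not depend on which of two sentences is applied once an event has occurred.

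**What to change.** Reconcile the two sentences of Section 12.1 with each other and with Section 7 by tying the exclusion to grade:

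- Do not count a symptom whose grade after SBRT is no higher than its recorded pre-treatment grade. Keep the unchanged oxygen requirement as the illustration.
- Count, and record on the toxicity form, any new Grade 3+ event and any rise from the pre-treatment grade to Grade 3 or higher, including 3 to 4, subject to the existing attribution test.
- Change the baseline and Grade 3-4 exceptions in Section 7, and the matching sentence in Section 9.1, so that they cover only events that have not risen above the pre-treatment grade.
- State that the pre-treatment adverse event assessment in Section 8 records a CTCAE grade for each symptom present.

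This needs no new visit, no new test and no change in sample size. The costs are a slightly higher recorded toxicity rate and some added attribution judgements, chiefly in separating treatment injury from disease progression.
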